6.1 Study Interventions Administered

Table 5 Study Interventions Administered

Study Intervention Name:	RSVPreF3 OA Investigational Vaccine		Prevnar 20/Apexxnar
Study intervention formulation	RSVPreF3 (120 µg)	AS01 _E : QS-21* (25 µg), MPL (25µg), liposomes; Water for injection	PS1(2.2 µg) ^{1,2} ; PS3(2.2 µg) ^{1,2} ; PS4(2.2 µg) ^{1,2} ; PS5(2.2 µg) ^{1,2} ; PS6A(2.2 µg) ^{1,2} ; PS6B(4.4 µg) ^{1,2} ; PS7F(2.2 µg) ^{1,2} ; PS8(2.2 µg) ^{1,2} ; PS9V(2.2 µg) ^{1,2} ; PS10A(2.2 µg) ^{1,2} ; PS11A(2.2 µg) ^{1,2} ; PS12F(2.2 µg) ^{1,2} ; PS14(2.2 µg) ^{1,2} ; PS15B(2.2 µg) ^{1,2} ; PS18C(2.2 µg) ^{1,2} ; PS19A(2.2 µg) ^{1,2} ; PS19F(2.2 µg) ^{1,2} ; PS22F(2.2 µg) ^{1,2} ; PS23F(2.2 µg) ^{1,2} ; PS33F(2.2 µg) ^{1,2} ; ¹ conjugated to CRM ₁₉₇ (51 µg); ² adsorbed on AlPO ₄ (0.125 mg Al ³⁺); Water for injections
Presentation	Vial; powder for suspension for injection	Vial; suspension for suspension for injection	Suspension for injection
Route of Administration	Intramuscular use		Intramuscular use
Product category	Biologic		Biologic
Type	Study		Study
Administration site			
Location	Deltoid		Deltoid
Laterality	Non-dominant		Co-ad group: Dominant Control group: Non-dominant
Number of doses to be administered	1		1
Dose Volume**	0.5 mL		0.5 mL
Packaging, labeling***	Refer to Pharmacy Manual for details		Refer to Pharmacy Manual for details
Manufacturer	GSK		Pfizer

Abbreviations: Al=aluminum; AlPO₄=aluminum phosphate; AS01_E=Adjuvant System 01; CRM=cross-reactive material; PS=pneumococcal serotype; QS-21=*Quillaja saponaria* Molina, fraction 21; MPL=monophosphoryl lipid A.

*Licensed by GSK from Antigenics Inc, a wholly owned subsidiary of Agenus Inc., a Delaware, USA corporation.

**Refer to the Pharmacy Manual for the volume after reconstitution.

***Labeling is compliant with the requirements of applicable regulatory agencies.

6.1.1 Medical Devices

There are no GSK manufactured medical devices (or devices manufactured for GSK by a third party) provided for use in this study. Other medical devices (not manufactured by or for GSK) provided for use in this study are: thermometer, syringe, needle, and pre-filled syringe for PCV20. All medical devices are CE marked and will be used for their intended use. Instructions for medical device use are provided in the package insert.

All device deficiencies (including malfunction, use error and inadequate labeling) shall be documented and reported by the investigator throughout the clinical investigation (see [Sections 8.3.6](#) and [10.3](#)) and appropriately managed by GSK.

6.2 Preparation, Handling, Storage, and Accountability

The investigator or designee must confirm appropriate temperature conditions have been maintained during transit for all study intervention received, and any discrepancies are reported and resolved before use of the study intervention.

Only participants enrolled in the study may receive study intervention, and only authorized study site staff may supply or administer study intervention.

All study interventions must be stored in a secure, environmentally controlled, and monitored (manual or automated) area in accordance with the labeled storage conditions with access limited to the investigator and authorized study site staff. The storage temperature should be continuously monitored and recorded with a calibrated (if not validated) temperature monitoring device(s).

The investigator, institution, or the head of the medical institution (where applicable) is responsible for study intervention accountability, reconciliation, and record maintenance (i.e., receipt, reconciliation, and final disposition records).

The investigator, a member of the study site staff, or a hospital pharmacist must maintain an adequate record of the receipt and distribution of all study interventions using the Drug Accountability Form. These forms must be available for inspection at any time.

Further guidance and information for the final disposition of unused study interventions are provided in the Pharmacy Manual.

6.3 Measures to Minimize Bias: Randomization and Blinding

6.3.1 Participation Identification

Participant identification numbers (IDs) will be assigned sequentially to the participants who have consented to participate in the study, according to the range of participant IDs allocated

to each study center. The participant IDs will be documented in the electronic Case Report Form (eCRF).

The eligibility of the participant will be determined based on the inclusion and exclusion criteria listed in [Section 5.0](#). The participant ID will be the participant's unique identification number for all eCRFs and associated study documentation that will be used for duration of the study. If the participant is terminated from the study, their participant ID cannot be re-assigned.

6.3.2 Randomization to Study Intervention

All eligible participants will be centrally randomized to the study group at a 1:1 ratio using Interactive Web Response System (IWRS) randomization (refer to [Glossary of Terms](#) for a definition of IWRS).

The participants will receive a unique intervention number (refer to [Glossary of Terms](#) for a definition of a treatment number). Once a treatment number has been assigned, it cannot be re-assigned.

6.3.3 Intervention Allocation to the Participant

Approximately 1090 eligible participants will be randomly (1:1) assigned to 2 study groups using a centralized randomization system on internet at Visit 1 (Day 1). The randomization algorithm will use a minimization procedure accounting for age (60 to 69, 70 to 79 or ≥ 80 years) and center. Minimization factors will have equal weight in the minimization algorithm.

After obtaining the signed and dated Informed Consent Form (ICF) from the participant and if the participant eligible, the delegated clinical trial staff will access IWRS. Upon entering the participant ID and age, the randomization system will determine the treatment group and provide the treatment number to be used for the trial intervention. The treatment number(s) to be used for subsequent dose administration(s) will be provided by the same IWRS.

Instructions related to instances when IWRS is not available will be provided to the site.

Refer to the IWRS user manual for additional information related to the treatment number allocation.

6.3.4 Allocation of Participants to Assay Subsets

Immunogenicity assessments are planned as outlined in [Section 8.1](#).

Refer to [Section 9.2](#) for descriptions of analysis populations.

6.3.5 Blinding and Unblinding

This is an open-label study. The participant and principal investigator will not be blind to the intervention administered.

The laboratory in charge of sample testing will be blinded to the study intervention assignment. Codes will be used to link the participant and study to each sample. There will be no link between the study intervention and the identity of the participant.

6.4 Study Intervention Compliance

When participants are dosed at the site, they will receive study intervention directly from the investigator or designee, under medical supervision. The mode of administration (i.e., intramuscularly), laterality, as well as the date and time of each dose administered in the clinic will be recorded in the source documents. See [Section 6.1](#) for details in intervention administration.

6.5 Dose Modification

Not applicable.

6.6 Treatment of Overdose

Any dose of any study vaccine greater than the one required per protocol is considered an overdose. All cases of vaccine overdose should be reported as protocol deviations. Any signs or symptoms resulting from an overdose should be reported as AEs, or SAEs if SAE criteria are met; overdose per se should not be reported as an AE/SAE. GSK does not recommend specific treatment for an overdose; however, any resulting adverse reaction should be treated symptomatically.

6.7 Concomitant Therapy

At each study visit/contact, the investigator or his/her delegate should question the participant and/or the participant's caregiver about all medications/products taken, and vaccinations received by the participant.

The following concomitant medication(s)/product(s)/vaccine(s) must be recorded in the eCRF:

- All concomitant medications including vaccines, except vitamins and dietary supplements, administered after the first dose of study intervention (Day 1 to EoS).
- All concomitant medications leading to discontinuation of the study intervention or elimination from the analysis, including products/vaccines (Refer to [Section 5.2.2](#) and [Section 9.2.1](#)).

- All concomitant medication which may explain/cause/be used to treat an SAE including vaccines/products, as defined in [Sections 8.3.1](#) and [10.3.6](#). These must also be recorded in the Expedited Adverse Event report.
- Any prophylactic medication (eg, analgesics, antipyretics) administered on the day of study vaccination in the absence of any symptom and in anticipation of a reaction to the vaccination.

The medical monitor should be contacted if there are any questions regarding concomitant or prior therapy.

7.0 DISCONTINUATION OF STUDY INTERVENTION AND PARTICIPANT DISCONTINUATION/WITHDRAWAL

Discontinuation of specific study sites or of the study as a whole are detailed in [Section 10.1.10](#).

7.1 Discontinuation of Study Intervention

Discontinuation of study intervention refers to any participant who has not received all planned doses of study intervention. A participant who discontinued study intervention may continue other study procedures (e.g., safety or immunogenicity), planned in the study protocol at the discretion of the investigator.

The primary reason for premature discontinuation of the study intervention will be documented on the eCRF as follows:

- Adverse event requiring expedited reporting to IQVIA
- Unsolicited non-serious adverse event
- Solicited adverse event
- Not willing to be vaccinated
- Other (specify)

If a participant who does not meet enrollment criteria is inadvertently enrolled, that participant must be discontinued from study intervention and IQVIA must be contacted. An exception may be granted in rare circumstances for which there is a compelling safety reason to allow the participant to continue. In these rare cases, the investigator must obtain documented approval from GSK, or designee, to allow the participant to continue in the study.

Participants who discontinue study intervention will not be replaced.

7.1.1 Contraindications to Subsequent Study Intervention Administration

The eligibility for subsequent study intervention administration in the control group must be confirmed before administering any additional dose.

Participants who meet any of the criteria listed below or criteria listed in [sections 5.2.1](#) and [5.2.2](#) should not receive additional doses of study intervention. Such participants should be encouraged to continue other study procedures, at the investigator's discretion ([10.3](#)). All relevant criteria for discontinuation of study intervention administration must be recorded in the eCRF.

- Participants who experience any SAE judged to be possibly or probably related to the first study intervention (PCV20 vaccine) and that, in the opinion of the investigator, may pose

additional risk to the participant if he/she receives the second study intervention (RSV investigational vaccine).

- Participants who develop any new condition which, in the opinion of the investigator, may pose additional risk to the participant if he/she continues to participate in the study.
- Anaphylaxis following the administration of study intervention(s) from Visit 1 onwards.
- Any condition that in the judgment of the investigator would make intramuscular injection unsafe.

7.2 Participant Discontinuation/Withdrawal from the Study

A participant may withdraw from the study at any time at his/her own request or may be withdrawn at any time at the discretion of the investigator for safety, behavioral, or compliance, or administrative reasons. This is expected to be uncommon.

A participant is considered to have withdrawn from the study if no new study procedure has been performed or no new information has been collected for him/her since the date of withdrawal/last contact.

From an analysis perspective, a study ‘withdrawal’ refers to any participant who did not return for the concluding visit/was not available for the concluding contact planned in the protocol.

Investigators/site designee will attempt to contact participants who do not return for scheduled visits or follow-up.

All data and samples collected up to and including the date of withdrawal of/last contact with the participant will be included in the study analyses.

The primary reason for study withdrawal will be documented in the eCRF, based on the list below:

- Adverse events requiring expedited reporting to IQVIA (see [Appendix 3](#) for details regarding such events)
- Unsolicited non-serious AEs
- Solicited event
- Withdrawal by participant, not due to an AE*
- Migrated/Moved from the study area
- Lost to follow-up
- Sponsor study termination
- Other (specify)

*If a participant is withdrawn from the study because he/she/the participant’s caregiver(s) has withdrawn consent and the reason for withdrawal was provided, the investigator must document this reason in the eCRF.

Participants who are withdrawn from the study because of AEs/SAEs must be clearly distinguished from participants who are withdrawn for other reasons. Investigator will follow participants who are withdrawn from the study due to an AE/SAE until the event is resolved (see [Appendix 3](#) for details regarding follow-up AEs).

7.3 Lost to Follow-up

A participant will be considered ‘lost to follow-up’ if he/she fails to return for scheduled visits and cannot be contacted by the study site.

The following actions must be taken if a participant fails to return to the clinic for a required study visit:

- The study site must attempt to contact the participant and reschedule the missed visit as soon as possible, counsel the participant on the importance of maintaining the assigned visit schedule and ascertain whether the participant wishes to and/or should continue in the study.
- Before a participant is deemed lost to follow-up, the investigator or designee must make every effort to regain contact with the participant (where possible, 3 telephone calls, and if necessary, a certified letter to the participant’s last known mailing address or local equivalent methods). These contact attempts should be documented in the participant’s medical record.
- Should the participant continue to be unreachable, he/she will be considered to have withdrawn from the study.
- Study site personnel, or an independent third party, will attempt to collect the vital status of the participant within legal and ethical boundaries for all participants randomized, including those who did not get study intervention. Public sources may be searched for vital status information. If vital status is determined as deceased, this will be documented, and the participant will not be considered lost to follow-up. Sponsor personnel will not be involved in any attempts to collect vital status information.
- If the participant indicates he/she does not want to continue with the study, he/she will be contacted for a final assessment for safety reasons; he/she will be withdrawn from the study with reason of “withdrawal of consent.

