9.1. Disposition

Participant disposition, withdrawals, and reasons for exclusion from each analysis set, including inclusion as well as exclusion criteria will be presented for the ENR. Participant disposition will be summarized for screen failures from SCR to ENR. Specifically, the number of participants, vaccinated, completed the study, discontinued from the study and the reason for discontinuation will be summarized by study intervention for the ENR. Additionally, the number of participants returning for each visit for the ES will be presented.

A listing of the disposition for all participants with early withdrawal or discontinuation will be provided.

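### Protocol Section 7.3 fixes the withdrawal reason as withdrawn consent even when an adverse event is the cause, which conflicts with Section 7.2

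*Protocol*

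**What the plan says.** Protocol Section 7.3 opens its list of steps with the trigger: "The following actions must be taken if a participant fails to return to the clinic for a required study visit". The last step reads: "If the participant indicates he/she does not want to continue with the study, he/she will be contacted for a final assessment for safety reasons". It then fixes the outcome: "he/she will be withdrawn from the study with reason of “withdrawal of consent".

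Protocol Section 7.2 has its own rule for the reason: "The primary reason for study withdrawal will be documented in the eCRF, based on the list below". The list has three AE entries (events needing expedited reporting, unsolicited non-serious AEs, solicited events). It also has "Withdrawal by participant, not due to an AE", loss to follow-up, moving away, sponsor termination and a free-text other category. A footnote to the participant-withdrawal entry covers a person who "has withdrawn consent and the reason for withdrawal was provided, the investigator must document this reason in the eCRF". The section adds: "Participants who are withdrawn from the study because of AEs/SAEs must be clearly distinguished from participants who are withdrawn for other reasons".

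SAP Section 9.1 carries the coded reason into the results: "the reason for discontinuation will be summarized by study intervention for the ENR".

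**The concern.** The two sections give different instructions for the same person. Take a participant who has a troublesome reaction, misses the next visit, is reached by the site and says that he or she is stopping because of the reaction. Section 7.2 calls for an AE code. Section 7.3 calls for withdrawn consent. That term is not an item on the Section 7.2 list, and the one entry the footnote ties it to states that no AE was the cause.

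Safety and reactogenicity of giving the two vaccines together or separately is a secondary objective. Withdrawal because of a reaction is a natural thing to read off the disposition table by group. If sites follow Section 7.3, that count can be too low.

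**Working it through.** The point is textual. The documents give no expected count or rate of AE-related withdrawals, so there is no figure of the plan to reproduce. The check compares the two sections and then follows an AE-driven refusal through data collection and reporting.

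**Step 1: the two rules side by side**

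| | Section 7.2 | Section 7.3, last step |
|---|---|---|
| Who | Any withdrawn participant | Missed a required visit, was reached, declines to continue |
| Reason recorded | Primary reason, from the list | One fixed reason |
| AE as cause | Three separate entries; must be distinguished | No exception |
| Withdrawn consent | Only in the footnote to the entry worded as not due to an AE | The fixed reason itself |

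The footnote requires a stated reason to be written down. It does not say that the coded primary reason then changes. So for an AE-driven refusal the literal Section 7.3 code contradicts Section 7.2.

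**Step 2: what is collected apart from the code**

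The schedules of activities (Protocol Tables 1 and 2) have a row at every visit and contact for AEs and SAEs leading to withdrawal. Protocol Section 8.3.1 collects them from first dose to discharge. The event and its link to withdrawal can therefore be in the database even when the disposition reason is wrong.

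**Step 3: what the SAP reports**

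- Unsolicited AEs leading to study discontinuation: tabulated by group (Section 16.1.2).
- SAEs leading to discontinuation: a listing and a tabulated listing (Section 16.1.4).
- pIMDs leading to study discontinuation: a tabulated listing (Section 16.1.5).
- Solicited events: Section 16.1.1 covers incidence, grade, medical attendance, duration, events ongoing after the 7-day period, and participant against investigator grading. It has no output for study withdrawal.

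For a non-serious solicited event, the disposition reason in SAP Section 9.1 is thus the only named output in which study withdrawal would show.

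Protocol Section 7.1 does record a reason for stopping the intervention, with a solicited-event option. That applies only to someone who has not received all planned doses. It gives nothing for a Co-ad participant, who receives both vaccines on Day 1, or for a Control participant who leaves after the second vaccination.

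**Step 4: sensitivity of the table**

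With about 545 participants planned per group, one miscoded participant moves a disposition row by 1/545 = 0.0018, about 0.18 percentage points. How many would be miscoded cannot be worked out from the documents.

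**Step 5: reach into the primary analysis**

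SAP Section 2.4 treats permanent discontinuation alike whatever its reason. The immunogenicity comparisons do not depend on the code.

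**The case against.** The best defence is that the sections can be read together. Section 7.2 alone speaks of the primary reason in the eCRF; Section 7.3 mentions neither. On this view Section 7.3 only separates people who cannot be reached from people who are reached and decline. A careful site would then apply the explicit Section 7.2 duty to distinguish AE withdrawals. That reading is possible, but Section 7.3 names a reason without qualification and does not refer back to the list, so a site that follows it to the letter is not misreading it.

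Other parts of the defence stand in full and rule out stronger readings that a reader might infer:

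- **AE withdrawals are hidden.** The documents do not support this. The events are recorded separately, Section 7.3 itself requires a safety contact, and the SAP reports unsolicited AEs, SAEs and pIMDs leading to discontinuation. It also lists the disposition of every early withdrawal.
- **The effect differs by arm.** The rule is the same in both groups. Control has one more site visit at which it could be triggered, but no figure in the documents shows a difference.
- **The list is closed.** It ends with a free-text category.
- **AE follow-up stops after the final contact.** Section 7.3 does not say so. The duties in Sections 7.2, 8.2, 8.3 and 8.3.3 remain, and one more safety contact does not cancel them.

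Reactogenicity rates do not depend on disposition coding, and withdrawal rate is not a listed safety endpoint.

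**Conclusion.** The conflict is real and its consequence is limited. Followed literally, Section 7.3 miscodes an AE-driven refusal after a missed visit. The disposition table by group can then undercount AE-related withdrawals and disagree with the AE outputs. The remaining gap is chiefly non-serious solicited events, for which the SAP names no other output of study withdrawal.

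The number affected cannot be derived from the documents. It is probably small, since Section 7.2 expects withdrawal to be uncommon and only those who first miss a visit fall under this rule. The conclusion assumes that sites apply the Section 7.3 wording as it stands. This is a minor correction that is worth making because the two instructions are adjacent and both are worded as requirements.

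**What to change.** In the last bullet of Section 7.3, replace the fixed reason with an instruction to record the primary reason selected from the list in Section 7.2. An AE, SAE or solicited event that is the primary reason is then coded as such. The wording should keep to the primary reason: an AE code triggered whenever an AE merely contributed would overcount and would itself depart from Section 7.2. Add to Section 7.3 that the AE follow-up described in Section 7.2 still applies in addition to the final safety contact.

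The cost is a sentence or two in the protocol and a line in the eCRF completion guidance. No new data field is needed, because the Section 7.2 list is already the one used in the eCRF.

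If the protocol can no longer be amended, use the data review before database lock (SAP Section 5.1). Compare participants coded as withdrawn by their own decision or by withdrawn consent with the AEs recorded as leading to withdrawal, and query any mismatch. This uses data already collected and changes no analysis.
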